6.7. Derived and Transformed Data

6.7.1. Age

Age, in completed years, at screening will be defined as:

Age (years) = integer value ($[(\text{Date Signed Informed Consent} - \text{Date of Birth} + 1) / 365.25]$)

6.7.2. Study Day

Study day will be calculated using the first investigational study drug (INP103 or placebo) administration date as the reference date. If the date of interest occurs on or after the first study drug administration date, then study day will be calculated as (date of interest – date of first study drug administration+1). If the date of interest occurs prior to the first study drug administration date, then study day will be calculated as (date of interest – date of first study drug administration).

Data listings will present study days in addition to assessment dates. The first day of dosing will be identified as Study “**Day 1**” per SDTM convention. There is no Study Day 0.

6.7.3. Change from Baseline

Change from baseline will be calculated as (post-baseline result – baseline result).

6.7.4. Observed Cases (OC) and Last Observation Carried Forward (LOCF), Missing Data and Outliers

Not applicable for this study.

6.7.5. Completers

Not applicable for this study.

6.7.6. Other Derivations

Body Mass Index (kg/m^2 , to one decimal place) = Body Weight (kg) / (Height^2 (m)).

For any observed original results above the upper limit or below the lower limit in laboratory assessment, the original results will be presented in data listing and the upper limit value or the lower limit value will be used for summary table. For example, *0.1* will be used if the original result is “<0.1”, while *1000* will be used if the original result is “>=1000”.

Treatment emergent adverse events will be defined as AEs which commence on or after the time of start of first study drug administration. AEs without an onset date or time will be defined as treatment emergent except if an incomplete date (e.g., month and year) clearly indicates that the event started prior to start of first study drug administration or if the AE stop date indicates that the event started and/or stopped prior to start of first study drug administration.

Adverse event time since study drug administration (in minutes) = (Onset Date + Onset Time) – (Study Drug Administration Date + Study Drug Administration Time).

Duration of AE (in minutes) = (Resolution Date + Resolution Time) - (Onset Date + Onset Time).

The response is defined as an improvement of $\geq 30\%$ in MDS-UPDRS Part III score from baseline to post INP103/Placebo dosing time point for each patient.

Time to response = (Time at FIRST response [as defined above] post study drug administration [INP103/Placebo] – Time at the first study drug administration [INP103/Placebo] [Unit = minutes]).

The orthostatic hypotension is defined as a reduction in systolic blood pressure of 20 mmHg or more, and/or a reduction in diastolic blood pressure of 10 mmHg or more, for the standing measurement compared to the supine measurement.

All AUC values will be calculated by using the trapezoidal rule.

7. TREATMENT COMPARISONS

7.1. Data Display Treatment and Other Sub-Group Descriptors

- All Placebo
- INP103 35 mg
- INP103 70 mg
- INP103 140 mg
- INP103 70 mg /7.0 mg carbidopa
- Overall

Note: All subjects randomized to placebo, from all cohorts, will be combined into a single placebo group (i.e. All Placebo Subjects).

8. GENERAL CONSIDERATIONS FOR DATA ANALYSES

The listings, figures and summary tables for the disposition, safety, PK, and PDyn data will be the responsibility of the study Biostatistician at CNS.

The currently supported version of SAS software will be used to perform all data analyses, excluding the estimation of PK parameters, which will be undertaken with WinNonlin. The actual SAS and WinNonlin versions used will be presented in the Clinical Study Report (CSR).

All data in the database will be presented in the data listings. Unless otherwise stated, all listings will be sorted by cohort, randomized treatment group, subject number and assessment date/time.

Unless otherwise stated, continuous variables will be summarized using descriptive statistics including number of non-missing observations, mean, standard deviation (SD), median, minimum and maximum values.

Categorical variables will be summarized with frequency counts and percentages. The population size (N for sample size and n for available data) and the percentage (of available data) for each class of the variable will be presented. Percentages will be rounded to one decimal place, with the denominator being the number of subjects in the relevant population, unless otherwise stated.

Only data from nominal protocol scheduled visits will be included in the summary tables. Data from unscheduled visits will not be included in the summary tables but will be included in the figures and listings.

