12.2. Analysis Populations

Safety Population: All subjects who receive any amount of INP103 or placebo will be included in the Safety Population. A pooled placebo group (of subjects from each of the five cohorts) will be used for comparisons. The data will be analysed according to the treatment received.

Benserazide Safety Population: All subjects who receive any amount of benserazide in Cohorts 1, 2 and 3 (as provided by the Sponsor) will be included in the Benserazide Safety Population. This population will be used for the analysis of the safety data collected after receiving benserazide (as provided by the Sponsor) and before receiving INP103 or placebo. This population will not be applicable to Cohort 4.

PK Population: All subjects who receive any amount of INP103 or placebo and have sufficient samples collected for non-compartmental analysis will be included in the PK Population. The data will be analysed according to the treatment received.

Intention-to-Treat (ITT) Population: All randomized subjects who have baseline and at least one post-dose assessment of motor function will be included in the ITT Population. A pooled placebo group (of subjects from each of the five cohorts) will be used for comparisons. The data will be analysed according to the randomized treatment group.

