6.4. Data Presentation Conventions

Continuous safety variables (e.g., clinical laboratory values, vital signs and ECGs) will be reported to the same precision as the source data. Derived variables will be reported using the same precision as the value(s) from which they were derived. For the reporting of descriptive statistics, the mean and median will be reported to 1 decimal place more than the source data; the minimum and the maximum values will be presented to the same precision as the source data and standard deviations (SD) will be reported to 2 decimal places more than the source data. The coefficient of variation (CV%), as a percentage (i.e., x100%), will always be reported to 1 decimal place.

Pharmacokinetic concentration data that are presented by the lab in significant digits will be reported as received from the bioanalytical lab in by subject listings.

For categorical/discrete variables, the frequency count and the percentage (of available data) for each class of the variable will be presented and will be displayed in the form XX (XX.X%) where the percentage is in the parentheses.

Date variables will be formatted as ddMMMyyyy for presentation (where day and year are numeric and the first three letters of month in letters). Time will be formatted in 24-hour time as HH:MM for presentation.

Extra measurements (such as unscheduled or repeat assessments) will not generally be included in summary tables but will be included in subject listings. They may be used if a scheduled measurement is missing and the timing of the extra measurement is deemed suitable. They will be used in summary tables which are not 'time specific', for example, summaries of maximum post dose values. In the data listings and summary tables presented as part of the CSR, scheduled assessments will be identified by the protocol specified nominal visit day and scheduled time point.

Wherever possible, data will be decimal aligned.

The tables, figures and listings shells and table of contents as part of this Statistical Analysis Plan (SAP) provide the expected layout and titles of the tables, figures and listings. Any changes to format, layout, titles, numbering, or any other minor deviation will not necessitate a revision to the SAP, nor will it be considered a deviation from planned analyses. Only true differences in the analysis methods or data

CONFIDENTIAL AND PROPRIETARY

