6.5.2. Intention-to-Treat (ITT) Population

All subjects who randomized into this study, regardless of receiving the study drug (INP103 or placebo) or not, will be included in this population. In general, all data listings and subject disposition, will be generated on this population except PK and PDyn results. Summaries of demographics, prior and concomitant medications will be produced using this population.

This definition of the ITT population differs from the definition provided in the protocol and will supersede the protocol definition.

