10. EFFICACY ANALYSES

The analyses of PDyn results will be treated as the exploratory analysis of preliminary efficacy in this study and all efficacy analyses will be conducted on the ITT population.

10.1. Change from baseline to 30 minutes post-dose in MDS-UPDRS Part III Score at Visit 3

For each subject, the individual scale from question 3.1 to 3.18 of MDS-UPDRS Part III questionnaire will be added as total score and it will be applied for following analysis of MDS-UPDRS Part III score.

The changes from baseline to 30 minutes post-dose in MDS-UPDRS Part III total score at Visit 3 will be summarized by treatment groups (INP103 35 mg, INP103 70 mg, INP103 140 mg, INP103 70 mg with 7.0 mg carbidopa, or placebo).

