10.3. Cumulative proportion of responders by post-dose time point

The cumulative proportion of responders will be summarized by post-dose time point (15, 30, 45, 60, 90 or 120 minutes for C1, C2 and C3; 30, 60, 90 or 120 minutes for C4) and treatment groups (INP103 35 mg, INP103 70 mg, INP103 140 mg, INP103 70 mg with 7.0 mg carbidopa, or placebo) using frequency tabulations. Subjects that achieve response will count as a responder for all subsequent time points regardless of a return to “<30% improvement” post achievement of response.

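### The SAP gives two incompatible denominators for responder percentages and section 10.3 does not choose; one of them lowers any non-zero placebo rate at 15 minutes by a quarter to a third

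*SAP*

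**What the plan says.** **Denominator.** SAP section 8 contains both rules in one paragraph. It first refers to "N for sample size and n for available data) and the percentage (of available data", and the next sentence gives percentages to one decimal place "with the denominator being the number of subjects in the relevant population, unless otherwise stated". SAP 6.4 sides with the first rule: "the frequency count and the percentage (of available data) for each class of the variable will be presented". SAP 10.3 asks for frequency tabulations of cumulative responders by time and treatment group and does not say what to divide by.

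**Population.** SAP 10 states that "all efficacy analyses will be conducted on the ITT population". SAP 6.5.2 defines that set as "All subjects who randomized into this study, regardless of receiving the study drug (INP103 or placebo) or not" and says that it replaces the protocol's definition. The protocol, section 12.2, was narrower: "All randomized subjects who have baseline and at least one post-dose assessment of motor function will be included in the ITT Population". SAP 6.5.2 also sets PK and pharmacodynamic results apart from the general use of this set, yet section 10 uses it for the pharmacodynamic endpoints and no other set is defined for them.

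**Groups and times.** SAP 7.1 combines placebo subjects from all cohorts. SAP 10.3 lists 15, 30, 45, 60, 90 and 120 minutes for Cohorts 1-3, but only 30, 60, 90 and 120 minutes for Cohort 4. It also carries responses forward: "Subjects that achieve response will count as a responder for all subsequent time points".

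**Undosed subjects.** SAP 4.2 allows randomization on the day before dosing and replacement of randomized subjects who are not dosed. SAP 4 says that subjects found ON on the dosing day are not dosed.

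**The concern.** The pooled placebo group includes Cohort 4 subjects with no Part III examination at 15 or 45 minutes, and the SAP's ITT set can include subjects with no post-dose examination at all. If the population default governs the responder table, these subjects stay in the denominator without being able to enter the numerator at 15 minutes. They are reported as non-responders without having been examined.

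The 35, 70 and 140 mg groups are all scheduled at 15 minutes, so the Cohort 4 gap depresses only the placebo figure they are read against. Fifteen minutes is also where a reader would look for evidence of rapid onset. Undosed subjects dilute whichever arm they were assigned to, for reasons unrelated to the drug. Because the SAP supports two rules, the table depends on which sentence the programmer follows.

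**Working it through.** The documents state no responder percentage or responder denominator, so there is no planned figure to reproduce. The check is direct arithmetic on the planned group sizes.

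**Inputs (SAP 4.2 and 10.3).** Placebo in Cohorts 1-3: 3 × 2 = 6. Placebo in Cohort 4: 2, maximum 3. Pooled placebo: 6 + 2 = 8, maximum 6 + 3 = 9. Placebo subjects scheduled at 15 minutes: 6. The responder counts *x* below are assumptions.

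**15 minutes, all randomized subjects dosed.** Available-data rule: *x*/6. Population rule: *x*/8 or *x*/9.

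| *x* of 6 | *x*/6 | *x*/8 | *x*/9 | Drop (points) |
|---|---|---|---|---|
| 0 | 0.0% | 0.0% | 0.0% | 0 |
| 1 | 16.7% | 12.5% | 11.1% | 4.2 to 5.6 |
| 2 | 33.3% | 25.0% | 22.2% | 8.3 to 11.1 |
| 3 | 50.0% | 37.5% | 33.3% | 12.5 to 16.7 |

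The relative reduction is the same for every non-zero *x*: 1 − 6/8 = 25%, or 1 − 6/9 = 33%.

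**Undosed subjects.** The documents give no number, so take 0, 1 or 2 in an active group with 6 dosed subjects. Under the population rule, 4 responders give 4/6 = 66.7%, 4/7 = 57.1% or 4/8 = 50.0%. In pooled placebo at 15 minutes with 3 responders, one undosed subject moves 3/8 = 37.5% to 3/9 = 33.3%, or 3/9 = 33.3% to 3/10 = 30.0% if Cohort 4 is expanded. The first case works against INP103 and the second works for it.

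**45 minutes.** A Cohort 4 placebo subject who responded at 30 minutes is still a responder at 45. Assume 2 of the 6 Cohort 1-3 placebo subjects have responded by 45 minutes, and let *b* be the number of the 2 Cohort 4 placebo subjects who responded at 30 minutes. The population rule gives (2 + *b*)/8:

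- *b* = 0: 25.0%
- *b* = 1: 37.5%
- *b* = 2: 50.0%

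Cohorts 1-3 alone give 2/6 = 33.3%, so the population figure can lie on either side.

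The available-data rule does not settle this time point. With *b* = 1, the Cohort 4 responder has a carried-forward status and the other Cohort 4 subject has no score. Three results can be defended: 3/8 = 37.5% (everyone), 3/7 = 42.9% (those with a status) and 2/6 = 33.3% (those examined).

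**A trap in the obvious repair.** Suppose 2 Cohort 1-3 and 2 Cohort 4 placebo subjects have responded by 30 minutes, with no new responders by 45. Dropping Cohort 4 from placebo only at 15 and 45 minutes takes the proportion from 4/8 = 50.0% at 30 minutes to 2/6 = 33.3% at 45. A cumulative proportion should not fall.

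**The case against.** The strongest reply is that the SAP can be read correctly as it stands. The sentence before the population default, and SAP 6.4, both say available data. The default yields where something else is stated. SAP 8.5.1 and 8.5.2 rule out imputation, SAP 6.1 requires tables to show how many subjects the data apply to, and 10.3 lists Cohort 4's times separately. On that reading the 15-minute denominator is 6, undosed subjects drop out, and the distortion is nil. This stands to the extent that a reader might infer that the SAP definitely counts unexamined subjects as failures and so favours INP103. The documents do not support that: the population rule is one of two stated rules, and at 45 minutes it has no fixed direction.

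The stakes are also limited. No INP103-placebo difference in responder rate is planned, SAP 3.3 sets no formal hypotheses, protocol 12.1 says that the study is not powered for between-group pharmacodynamic comparisons, and the responder table has priority 2. One placebo subject among 6 is worth 16.7 points, so most shifts in the table above amount to less than one patient. The primary motor time point is 30 minutes, when every cohort is assessed.

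Finally, the SAP changed the ITT definition openly, and protocol section 12 lets the SAP prevail. Restoring the protocol's definition alone would not solve the Cohort 4 gap.

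These points do not remove the contradiction. Section 10.3 states no alternative to the default, applying the default literally gives a wrong 15-minute figure, and the available-data rule leaves 45 minutes open.

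**Conclusion.** The concern holds as an unresolved contradiction with a calculable consequence. If the population rule is applied, any non-zero 15-minute placebo responder rate is 25% lower in relative terms with 8 pooled placebo subjects and 33% lower with 9. If the available-data rule is applied, the 15-minute problem disappears. The percentage-point size depends on assumed counts: none with 0 responders, and 4.2 to 16.7 points with 1 to 3 of 6.

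The effect of undosed subjects is conditional on there being any, and its direction depends on their arm. At 45 minutes the plan does not determine the placebo figure under either rule.

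The endpoint is secondary and descriptive, and the Cohort 4 gap does not affect the 30-minute primary motor time point. The matter is worth correcting because the repair is cheap and the early placebo column is easily misread.

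**What to change.** 1. In SAP 10.3, state as an explicit exception to the general rule that the denominator at each time is dosed subjects with a baseline and at least one post-dose Part III score who were scheduled for Part III at that time.
2. Show a Cohorts 1-3 placebo column at all six time points, and all-pooled placebo at 30, 60, 90 and 120 minutes only. Each column then keeps the same subjects throughout, so a cumulative proportion cannot fall.
3. Print n at every time point.
4. Keep the all-randomized set for disposition and listings.
5. Reconcile the two sentences in SAP section 8 without deleting the population denominator. Other tables, such as adverse event incidence in SAP 11.1, need it.

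The cost is some SAP wording, one extra table column, and an efficacy set for this endpoint that is no longer all-randomized.

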6.4.5. Vital Signs

Subjects should be resting in a supine position for at least 3 minutes prior to and during vital signs measurement obtained. Blood pressure, heart rate, respiration rate and temperature should be measured when the subject is supine. Immediately following supine vital signs assessments, blood pressure only will be measured again when standing. When the time of vital signs measurement coincides with a

blood draw, the vital signs will be taken after the scheduled blood draw, while ensuring the blood draw is within the window specified in the protocol. When vital signs and other safety assessments occur at the same timepoints, clinic staff may follow the sequence of their usual standard practice.

Additional vital signs may be performed at other times if deemed necessary.

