8.5.3. Additional/Unscheduled Assessments and Missing Data

Generally, missing dates/times will not be imputed. Adverse events with missing or partial dates will be handled such that in the absence of contradictory information an AE is treatment emergent. For a missing start date (where the stop date is after the date of first study drug administration) the start date will be imputed as the first study drug administration date. Similarly, for a missing stop date, the stop date will be imputed as the date of last visit. If a partial date is recorded, the following convention will be used to assign the AE:

- If a start date is missing the day information and the month/year is the same as the first study drug administration date, then use the first study drug administration date, else '01' will be used for the day. If a start date is missing the month and the year is the same as the first study drug administration date, then use the first study drug administration date, else 'January' will be used for the start month.
- If a stop date is missing the day information and month/year is the same as the last study date, then use the last study date, else the last day of the given month will be used for the stop day. If a stop date is missing the month and the year is the same as the last study date, then use the last study date, else 'December' will be used for the stop month.

Extra measurements (such as unscheduled or repeat assessments) will not generally be included in summary tables but will be included in subject listings. They may be used if a scheduled measurement is missing and the timing of the extra measurement is deemed suitable. They will be used in summary tables which are not 'time specific'; for example, summaries of maximum post dose values.

The original data will always be presented in the listings.

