11.6. ECG Evaluations

All individual ECG parameter values (Heart Rate [bpm], QT interval [msecs], PR interval [msecs], QRS interval [msec], RR interval [msecs], QTcF [msecs], and QTcB [msecs]) and overall ECG clinical interpretation will be presented in data listing. Observed ECG parameter values and changes from baseline (prior to the first study drug administration [benserazide or INP103/placebo]) will be summarized by treatment and protocol specified collection time point.

In addition, clinical assessment of the ECG (Normal, Abnormal NCS, and Abnormal CS) will be summarized by cohort and treatment group and protocol specified collection time point, using frequency tabulations.

Furthermore, the proportion of subjects meeting the following criteria based on QTc values (defined both using the correction by Bazett and by Fridericia) will be summarized by treatment group, using frequency tabulations:

- QTc value >500 msec
- QTc value increasing >15% from baseline if baseline value is ≥ 440 msec
- QTc value increasing >30% from baseline if baseline value is <440 msec
- QTc value increasing >30% from baseline
- QTc value increasing >60% from baseline

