11.7.3. Orthostatic hypotension

The proportion of subjects experiencing orthostatic hypotension will be summarized by cohort and treatment group and protocol specified collection time point, using frequency tabulations, if applicable.

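### The SAP has two conflicting rules for unscheduled measurements in summary tables; the QTc-criteria counts depend on which is followed, and other unscheduled abnormal values reach listings only unless recorded as adverse events

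*SAP*

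**What the plan says.** **SAP 8** gives a rule with no exception, in two consecutive sentences: "Only data from nominal protocol scheduled visits will be included in the summary tables", followed by "Data from unscheduled visits will not be included in the summary tables but will be included in the figures and listings".

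**SAP 6.4** gives a softer rule: "Extra measurements (such as unscheduled or repeat assessments) will not generally be included in summary tables but will be included in subject listings". Two exceptions follow, and SAP 8.5.3 repeats both. The first is permissive: "They may be used if a scheduled measurement is missing and the timing of the extra measurement is deemed suitable". The second is mandatory and concerns tables without a specific time: "They will be used in summary tables which are not" time specific, with maximum post-dose values as the example.

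**SAP 11.6** sets out the QTc threshold criteria without a time point: the counts, under both the Bazett and the Fridericia correction ("Fridericia) will be summarized by treatment group, using frequency tabulations"), go by treatment group alone.

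**SAP 11.7.3** is different: "The proportion of subjects experiencing orthostatic hypotension will be summarized by cohort and treatment group and protocol specified collection time point". SAP 11.4, 11.6 and 11.7.4 use the same by-time-point layout for clinically significant laboratory results, the clinical assessment of the ECG, and new abnormal physical findings.

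**The SAP synopsis and Protocol 12.3** state the proportions with orthostatic hypotension, abnormal ECGs and abnormal physical findings by treatment group and name no time point.

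The protocol expects extra measurements. On blood pressure and the other vital signs, Protocol 6.4.5 says: "Additional vital signs may be performed at other times if deemed necessary". Protocol 6.4, 6.4.3 and 6.4.7 allow for additional safety measurements, physical examinations and laboratory tests.

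**The concern.** Safety and tolerability are the primary endpoint, over the 240 minutes after dosing and the 7 days of follow-up. Extra readings tend to be taken when someone is worried about a subject, so they are more likely than scheduled ones to be abnormal. A rule that keeps them out of the tables pushes the counts downward. With six active subjects in most groups, one subject is a visible share of the group.

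Two separate things are at stake. One is a contradiction: two programmers following the SAP could produce different QTc-criteria tables, and neither would have departed from the plan. The other is a layout choice: a table arranged only by scheduled time point has no cell for a reading taken at another time, whichever rule applies.

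**Working it through.** The plan states no figure on this point, so there is none to reproduce. The check sets the sections side by side and asks, for each safety summary, where an unscheduled post-dose value would go.

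**Step 1: is there a precedence rule?** Protocol 12 lets the SAP override the protocol. That does not settle a conflict inside the SAP, and the SAP does not rank section 8 against 6.4 and 8.5.3. Other sentences in SAP 8 carry an unless-otherwise-stated qualifier; these two do not.

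**Step 2: trace an unscheduled value.**

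| Summary | Layout in SAP 11 | Under SAP 8 | Under SAP 6.4 / 8.5.3 |
|---|---|---|---|
| QTc criteria (11.6, Table 14.3.6.3) | Treatment group, no time point | Out | In |
| ECG clinical assessment (11.6) | By time point | Out | Out, unless it replaces a missing scheduled value |
| Orthostatic hypotension (11.7.3) | By time point | Out | Out, unless it replaces a missing scheduled value |
| New physical findings (11.7.4) | By time point | Out | Out, unless it replaces a missing scheduled value |
| Clinically significant laboratory results (11.4) | By time point | Out | Out, unless it replaces a missing scheduled value |

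The contradiction therefore changes the QTc-criteria table and the replacement option. In the other four rows the by-time-point layout does the excluding. For three of those four (ECG assessment, orthostatic hypotension, physical findings) the SAP synopsis and Protocol 12.3 name no time point. On that wording the summaries are not time specific, and 6.4/8.5.3 would admit the extra values.

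**Step 3: size for the QTc table.** Suppose one subject's only QTc above 500 msec is on an unscheduled ECG, and all randomized subjects are dosed. The share is 1/n under 6.4/8.5.3 and 0/n under SAP 8.

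- Active group in Cohorts 1 to 3, n = 6: 0/6 = 0% against 1/6 = 16.7%.
- Cohort 4 active at its maximum, n = 9: 0% against 1/9 = 11.1%.
- Pooled placebo, n = 2 + 2 + 2 + 2 = 8: 0% against 1/8 = 12.5%.
- Pooled placebo with Cohort 4 at its maximum, n = 2 + 2 + 2 + 3 = 9: 0% against 1/9 = 11.1%.

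**Step 4: when could such values arise?** Protocol Table 1, 7.4.3 and 7.5 schedule post-dose vital signs at 30, 60 and 120 minutes and at Visit 4, and post-dose ECGs at 120 minutes and at Visit 4. The 120-minute readings may run to 180 minutes. Any reading between the 120-minute set and Visit 4 is therefore unscheduled, although that interval lies within the primary endpoint's 240 minutes and 7 days.

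**Step 5: does the adverse event route catch them?** In part. Protocol 8.4 requires abnormal findings that are clinically significant, or that come with signs or symptoms, to be recorded as adverse events if they meet that definition; post-dose events then enter the TEAE tables. Protocol 8.4 also says that abnormal findings are not adverse events in themselves. Under Protocol 8.5 the entry normally gives the diagnosis or symptom, and the finding itself only when neither is available. An asymptomatic standing drop of 20 mmHg that is not judged clinically significant would reach listings only.

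**The case against.** The best answer is that the important cases are already covered. A value found because a subject was unwell comes with signs or symptoms, so it is recorded as an adverse event if it meets the definition, and it is then tabulated. Every value is listed, for only 32 to 36 subjects, and safety is summarized without inferential testing. This stands, and it rules out the stronger reading that such a value could vanish from every safety table. What can be lost is the measured value from the QTc and orthostatic hypotension counts, and any abnormal value that never becomes an adverse event.

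A second answer is that SAP 8 speaks of visits while 6.4 and 8.5.3 speak of assessments. An extra ECG during the in-clinic stay belongs to scheduled Visit 3 and could be admitted without contradiction. That is a fair partial reconciliation. The SAP does not state it, however, and it leaves an ECG from an unscheduled visit in conflict.

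A reader might also infer that the contradiction is what removes blood pressure and laboratory values. It is not: those tables leave extra values out under both rules, apart from replacement.

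Finally, a reader might infer that the suitability clause lets values be chosen once results are known. The documents do not say so. The criterion is the timing of the measurement, not its value, and no section says the judgement is unblinded. What stands is that suitable timing is undefined, that SAP 8.5.4 applies no windows to fall back on, and that SAP 5.1 allows the sponsor to request unblinded interim results for Cohorts 1 and 2.

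**Conclusion.** The point holds in two limited parts. First, SAP 8 conflicts with SAP 6.4 and 8.5.3, and nothing in the documents resolves it. The consequence falls on the QTc-criteria table, where one subject is 0/6 or 1/6 (16.7%), and on whether an extra value may replace a missing scheduled one. Second, the by-time-point layout in SAP 11.4 to 11.7 generally leaves unscheduled abnormal values in listings alone unless they are recorded as adverse events, and for three summaries it is narrower than the SAP synopsis and Protocol 12.3. The subject-level counts for the primary safety endpoint can then be too low, not too high.

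The percentages are illustrations for a single subject. The documents do not say how many unscheduled readings to expect, so the likely number of omitted events cannot be estimated. The direction of the error rests on the assumption that extra readings are taken mainly where there is concern. It is worth correcting because it is cheap and concerns the primary endpoint; it does not undermine the safety analysis as a whole.

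**What to change.** 1. Replace both SAP 8 sentences. Removing only the second would leave the first, and the conflict with it. Put the 6.4/8.5.3 rule in their place and word it identically in all three sections: by-time-point rows use scheduled values; subject-level any-time post-dose counts use every post-dose value, scheduled or not.
2. Apply the any-time rule explicitly to the QTc criteria.
3. Add an any-time post-dose row, counted by subject, for orthostatic hypotension, clinically significant ECG results, clinically significant laboratory results and new abnormal physical findings. This also brings SAP 11 into line with the SAP synopsis and Protocol 12.3 for the summaries they state without a time point.
4. Replacement of a missing scheduled value may stay. If it does, define the acceptable timing window in the SAP before any unblinding.

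The cost is SAP wording and a few added table rows. The any-time counts will include unscheduled tests from local laboratories alongside central-laboratory results, and readings taken after usual PD medication resumes at 120 minutes. Both should be footnoted so that the counts are not read as effects of INP103 alone.
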